TELE-HEALTH FOR ALCOHOL AND SMOKING CESSATION, a proactive tele-health intervention that will provide controls for therapist, medication, time and attention effects. The tele-health intervention provides the same evidence-based telephone CBT for alcohol and smoking cessation, and tele-medicine clinic for access to smoking cessation pharmacotherapy as in the mCM intervention, but does not include mCM. Instead, participants will receive monetary compensation for each assessment, regardless of abstinence (\$3.00 for breathalyzer, \$1.00 for CO). No escalating or reset contingencies will be used to alter monetary compensation amounts in this group. Mobile assessments of abstinence will occur on the same schedule as the tele-health mCM condition.

C.9.2. Participant Recruitment, Eligibility, and Screening

A total of 55 participants with AUD and smoking will be enrolled across the three cohorts. Participants will be recruited from primary care and substance abuse clinics at

Duke University. We will also post flyers at local hospitals and in community settings. To allow more detailed analysis of the tele-health mCM intervention that is the focus of this study, the pilot trial conducted with the third cohort will randomize 30 participants to the tele-health mCM intervention, and 15 to the tele-health smoking cessation comparison condition.

Completers of the proposed tele-health mCM intervention will provide self-report data and evaluative feedback during an in-depth interview administered at the end of treatment, and described in the Assessments section below. Content analysis of the resulting data will evaluate study components (i.e., mCM procedures, CBT, interface with smart phone app, NRT utility and adherence) and subcomponents (e.g., mCM feasibility, CBT burden) that they address and the evaluations drawn (e.g., CBT session too long, video upload still unclear after mCM training). We will explore sociodemographic, substance use, and psychiatric comorbidity variables to examine the magnitudes of their associations with treatment retention and outcomes. This will identify areas of the treatment potentially in need of modification or enhancement to maximize its effectiveness. A summary of the findings will be evaluated by our team of clinical researchers (Drs. [name], [name], [name]), all of whom are experienced in treatment development and trial design, will evaluate a summary of the findings and determine changes to make to the intervention.

Recruitment

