Pharmacotherapy for Smoking Cessation

Treatment will include standard pharmacotherapy for smoking cessation. This consists of bupropion, nicotine patch, and an 8-week course of < 2 rescue methods (e.g., nicotine gum, lozenge) in participants for whom these medications are not contraindicated or who receive medical clearance from a physician. Participants will be screened for suitability for NRT or other smoking cessation medication. Participants who report being contraindicated to bupropion or NRT (i.e. high blood pressure not controlled by medication) must obtain authorization from their physician prior to receiving the corresponding medication. If the patient does not have a physician, or the physician does not respond to information requests, [name] will make determinations about whether to authorize study medications. [name] will prescribe a tailored amount and delivery type of NRT based on number of cigarettes smoked per

day, quit history, medical conditions, and psychiatric comorbidities. NRT and bupropion will be provided *via* mail. [name] will write the NRT and/or bupropion prescriptions and work with other study staff and participants' primary care physician to discuss contraindications. Eligible participants will be provided bupropion for eight weeks. Participants will be informed that they can discuss whether or not to continue bupropion use for relapse prevention with their personal physician. At the end of the study's course of bupropion, participants will be reminded to confer with their physician re: continued bupropion use. For participants who relapse to smoking or are unable to quit, [name] will make decisions about whether to prescribe additional NRT to assist the participant in their continued attempts to stop smoking.

6-Month Follow-Up

All participants will be asked to provide a saliva sample to bioverify smoking abstinence. Alcohol abstinence will be measured by self-report, breathalyzer, and a blood spot sample that measures PEth at the 6-month follow-up. Participants will be encouraged to attend the 6-month follow-up assessment in the lab. However, if participants are unable due to transportation issues or decline to attend the 6-month follow-up, we will administer interview and questionnaire measures by phone and collect saliva samples by mail.

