Self-reported and bioverified prolonged abstinence from alcohol, smoking, and dual abstinence at the 6-month follow-up will be the primary end-point. Prolonged abstinence will exclude substance use in the first two weeks following the quit date to give participants time to achieve initial abstinence (Hughes et al., 2003). Self-reported prolonged abstinence will be verified by breathalyzer alcohol assessment and assay of cotinine, a metabolite of nicotine in the saliva. Saliva samples will be collected from participants at end of treatment, and at 6-month follow-ups. Deidentified saliva samples will be sent to Salimetrics, and there they will be analyzed for the presence of cotinine using a standard cut point of 10 ng/ml to determine abstinence. A blind sample of 5% will be run again to assure test accuracy of saliva samples. All participants will be asked to provide saliva samples. However if it seems likely that they will have a positive saliva cotinine according to the Tobacco Exposure Questionnaire administered at end of

monitoring at 6-month follow-up, the collected sample may not be sent to Salimetrics for testing.

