Participants will also report alcohol consumption patterns such as standard drinks/week, heavy drinking episodes (drinking enough so that BrAC would have reached 0.08g/dL), proportion of days abstinent, and achieving recommended drinking limits (≤ 14 drinks/wk and < 5 drinks/day for men; ≤ 7 drinks/wk and < 4 drinks/day for women). Because bioverification of long-term alcohol abstinence is not substantially more reliable than self-report (Babor, Steinberg, Anton, & Del Boca, 2000), alcohol outcomes will primarily be assessed with self-report. Participants will provide breathalyzer verification of alcohol abstinence at the end of Thinning mCM and 6-month follow-up visits. Participants will also report number of cigarettes smoked each day, and days of smoking abstinence. Collection of alcohol and smoking use data will allow for calculation of dual abstinence days and longest duration of dual abstinence. Participants will be asked to submit a saliva sample for biochemical validation. Saliva will be stored in a freezer in a locked office. At the end of the study, the project coordinator will personally mail all saliva samples to the appropriate laboratory to be analyzed for the presence of cotinine. The saliva will only be tested for cotinine, a by-product of nicotine. This method yields response rates that are comparable to in-person collection methods (i.e., 70%). A standard cut-point of 10 ng/ml will be used to discriminate those who are abstaining from those who are continuing smokers.

Prolonged abstinence from alcohol will be assessed using phosphatidylethanol (PEth) as a biomarker at the 6-month follow-up visit. While self-report abstinence has been a proven indicator, bioverification using PEth testing is an effective tool for identifying heavy drinking (Nanau & Neuman, 2015), and has a 99% sensitivity for detecting excessive alcohol consumption (Aradottir et al., 2006). This will be assessed using a dried blood spot collection, collecting 3 spots (about 3 mL) of blood from the participants' finger. PEth testing has been shown to have. The de-identified test card will be collected by ARCpoint labs of Raleigh Durham for analysis. All sharps and biohazardous material will be collected and disposed of by ARCPoint labs.

Data Analyses

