Descriptive statistics will be used to summarize all study variables. For continuous variables, means, standard deviations, percentiles, ranges, box plots and histograms will be generated. For categorical variables, frequencies and proportions will be generated. We will construct individual and mean trajectory plots of the longitudinal outcome variables to understand their general trends over time (i.e., post-treatment, 6 weeks and 6 months). Differences in treatment outcomes will be tested via generalized linear modeling. In addition, we will explore the variability and correlation structure of longitudinal variables. We will examine all variables to determine if parametric distributional assumptions (e.g. normality for the continuous variables) are valid. Variables not meeting distributional assumptions will either be transformed or modeled

using nonparametric or semi-parametric methods (e.g. quasi-likelihood methods). In planning a full RCT of the tele-health mCM intervention for AUD and smoking, it is important to evaluate study feasibility and treatment procedures, as well as gain information about effects on proposed outcome variables.

Specific Aim 1: Develop a multi-component alcohol and smoking tele-health mCM intervention.

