We will additionally explore differences in alcohol and smoking abstinence outcomes by treatment. Because the tele-health only intervention is expected to have a uniformly small impact on alcohol and smoking outcomes in comparison to the tele-health mCM intervention, implementation of an imbalanced-samples design, with twice as many participants randomized to the tele-health mCM treatment as to the tele-health only treatment, should maximize power for identifying treatment effects. That said, the proposed sample has 80% power to detect a treatment effect equivalent to Cohen's $d = 0.76$. For reference, in our pilot study of 22 smokers with PTSD, tele-health mCM yielded an effect size of Cohen's $d = 0.79$ at the 3-month follow-up. In particular, comparisons by treatment at post-intervention, 6 week follow-up, and 6-month follow-up will be made regarding alcohol consumption (drinks/week, number of heavy drinking episodes, proportion of days abstinent, and achieving recommended drinking limits) and smoking (number of cigarettes smoked each day and number of days of smoking abstinence) *via*

generalized linear modeling, which can accommodate normally and non-normally distributed (e.g., count) variables.

References

- Acuff, S. F., & Murphy, J. G. (2017). Further examination of the temporal stability of alcohol demand. *Behavioural Processes, 141*, 33-41. doi:10.1016/j.beproc.2017.03.020.
- Alessi, S. M., & Petry, N. M. (2013). A randomized study of cellphone technology to reinforce alcohol abstinence in the natural environment. *Addiction, 108*(5), 900-909. doi:10.1111/add.12093
- drinking outcomes in clinical trials. *Journal of Studies on Alcohol, 61*, 55-63.
- Bechara. A., Damasio, A.R., Damasio, H., Anderson, S.W. (1994). Insensitivity to future consequences following damage to human prefrontal cortex. *Cognition, 50*, 7-15.

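### The stated 80% power at d = 0.76 is not delivered by 30 v 15 and allows for no loss, and the phone/mail 6-month route leaves alcohol and dual abstinence unverified with no rule for classifying such cases

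*Combined protocol and SAP*

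**What the plan says.** **Design.** Participant Recruitment, Eligibility, and Screening says that "the pilot trial conducted with the third cohort will randomize 30 participants to the tele-health mCM intervention, and 15 to the tele-health smoking cessation comparison" arm. That is 45 of the 55 enrolled across the three cohorts.

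**Power.** Under Data Analyses, Specific Aim 2, "the proposed sample has 80% power to detect a treatment effect" of Cohen's d = 0.76. No sample size, alpha, sidedness, outcome or attrition term is attached. The sentence sits in a paragraph on exploring abstinence differences by treatment, which goes on to list consumption and day-count outcomes. On method, Data Analyses says that "Differences in treatment outcomes will be tested via generalized linear modeling". The only buffer for loss is before enrolment: Recruitment expects 70 consents to yield 55 enrolled.

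**Primary end-point.** Outcome Measurement and Biochemical Verification says that "Self-reported and bioverified prolonged abstinence from alcohol, smoking, and dual abstinence at the 6-month follow-up will be the primary end-point". Self-report is to be checked by breathalyzer for alcohol and by saliva cotinine for smoking. The same section adds a PEth blood spot for alcohol at 6 months. It tests saliva for cotinine only and says that alcohol outcomes rest mainly on self-report. Of saliva collection it says: "This method yields response rates that are comparable to in-person collection methods (i.e., 70" percent).

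**Remote route.** Under 6-Month Follow-Up, for anyone who cannot or will not attend, "we will administer interview and questionnaire measures by phone and collect saliva samples by mail". No alcohol test is listed. Table 1 and Mobile CM Procedures have the breathalyzer returned at the end of monitoring, and Table 1 lists the blood spot only at the Session 8 lab visit.

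**The concern.** There are two linked problems.

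First, the one sensitivity figure in the plan looks too good for the design it describes, and it assumes that every randomized participant contributes. The pilot is meant to support a grant application, so an overstated power figure would be carried into the planning of the next trial and into the reading of a null result here.

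Second, the alternative offered to people who do not attend at 6 months keeps the smoking check but drops both alcohol checks. Two of the three parts of the primary end-point (alcohol and dual) then have no biochemical confirmation for a remote participant who reports abstinence. Without a classification rule the analyst must choose afterwards between accepting the claim, excluding the person and counting the person as not abstinent. Accepting the claim mixes verified and unverified abstinence under one label. The arms are small, so each such decision matters: one person is 1/15 = 6.7 percentage points in the comparison arm and 1/30 = 3.3 points in the mCM arm.

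**Working it through.** **Inputs.** From the documents: n = 30 and 15; d = 0.76; stated power 80%; saliva response 70%. Assumed, because the plan gives neither: alpha 0.05, with both one- and two-sided tests tried.

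**Formula.** Two-sample t-test with noncentrality λ = d × √(n1·n2/(n1+n2)) and df = n1 + n2 − 2. Power is the probability that a noncentral t exceeds the critical value.

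**Step 1: the plan's own figure, full follow-up.** For 30 v 15, √(450/45) = 3.162, so λ = 0.76 × 3.162 = 2.403 with df = 43.
- Two-sided (critical value 2.017): power 65.2%; d detectable at 80% power is 0.91.
- One-sided (critical value 1.681): power 76.4%; detectable d is 0.80.

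The normal approximation gives 67% and 78%. None of these reproduces 80%.

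**Step 2: what would reproduce it.** These variants come close to 80% at d = 0.76:
- 45 split equally, one-sided t: 80.6%.
- All 55 as 40 v 15, one-sided t: 79.8%.
- All 55 split equally, two-sided: 80.5% (normal) or 79.0% (t).

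None of them is the 30 v 15 randomized comparison.

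**Step 3: with 70% evaluable.** This assumes equal loss in the two arms and an analysis restricted to those with a sample. 0.70 × 30 = 21 and 0.70 × 15 = 10.5, so take 10 or 11.

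| Evaluable | λ at d = 0.76 | Power, two-sided | Power, one-sided | Detectable d at 80%, two-sided | Detectable d at 80%, one-sided |
|---|---|---|---|---|---|
| 30 v 15 | 2.403 | 65% | 76% | 0.91 | 0.80 |
| 21 v 11 | 2.042 | 51% | 64% | 1.08 | 0.95 |
| 21 v 10 | 1.978 | 48% | 61% | 1.11 | 0.98 |

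The loss scenario costs 14-17 points two-sided. The gap between 80% and 65% is there before any loss. Even taking the plan's 80% at face value, cutting information to 70% lowers power to about 65-67% and moves the detectable d to 0.76/√0.7 = 0.91.

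**Step 4: which checks exist by route at 6 months.**

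| Part of the primary end-point | Check, lab visit | Check, phone/mail |
|---|---|---|
| Smoking | saliva cotinine | saliva cotinine (mailed) |
| Alcohol | breathalyzer, PEth | none listed |
| Dual | both of the above | smoking part only |

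A person who reports drinking or smoking is non-abstinent on that substance without any sample. The gap therefore concerns self-reported abstainers who lack the required test. The documents give no expected share of remote visits, so their number cannot be computed.

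**The case against.** Several points on the other side have force.

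- A reader might infer that the trial was powered on all 45 for the bioverified end-point, and that this end-point cannot be obtained for that sample. The documents do not support this. The power sentence names no N and no outcome, and it leads into self-report measures that can be collected by phone. Lab attendees receive every test, and self-reported users need none. This stands.
- The 70% describes a collection method. The trial pays 50 dollars for the 6-month saliva sample and may do better. This stands: 70% is a scenario here, and it bears only on an analysis that needs a sample.
- The plan says alcohol outcomes rest mainly on self-report, because bioverification is held to be not much more reliable. That lowers the importance of a missing test. It does not remove the problem, since the same section puts bioverification into the primary end-point and adds PEth.
- A baseline-adjusted model could be more sensitive than a plain t-test. Reaching d = 0.76 two-sided at 30 v 15 would need a baseline correlation of about √(1 − (0.76/0.906)²) = 0.54. The plan states no such adjustment or correlation. Adjusting for the baseline value could not help for abstinence itself, as everyone must be drinking and smoking at entry.
- A reader might infer bias between arms, because only mCM participants are paid for abstinence. Those payments end about five weeks after the quit date, and the 6-month payments in Table 1 are the same for both arms. Differential use of the remote route is not shown.
- This is a feasibility pilot and the comparison is described as exploratory. That limits the severity. However, the Stage 3 section calls efficacy the trial's primary goal, and a primary end-point is named.

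**Conclusion.** The point holds in two parts.

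The power sentence is wrong as written for the planned comparison. At 30 v 15 with nobody lost, power at d = 0.76 is about 65% two-sided or 76% one-sided, not 80%. The sentence also makes no allowance for loss; 70% evaluable would take it to about 48-51% or 61-64%. These figures assume alpha 0.05, an unadjusted t-test and, for the loss scenario, equal loss in both arms and a complete-case analysis. The shortfall at full follow-up is separate from non-response and should not be attributed to it.

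The remote 6-month route leaves the alcohol and dual parts of the primary end-point unverified for self-reported abstainers, and the plan does not say how to count them. The size of this gap is unknown because the remote share is not stated. The finding is one of missing specification; neither a bias between arms nor an unobtainable end-point is shown. Both parts should be corrected, and both can be corrected in the text.

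**What to change.** 1. **Data Analyses, Specific Aim 2.** Restate the power, or preferably the detectable effect, for 30 v 15. Give alpha, sidedness, the test and the outcome it refers to. Add one line under an explicit loss assumption such as 70% evaluable (21 v 10 or 11). If the 80% came from an adjusted model or another split, say so and give its inputs.

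2. **Outcome Measurement and Biochemical Verification, and 6-Month Follow-Up.** Name the sample or samples required for each part of the end-point, including whether alcohol needs the breathalyzer, PEth or both. Count any self-reported abstainer without the required sample as not bioverified-abstinent, identically in both arms and whatever the route. Keep all 45 in the denominator. Report self-reported abstinence alongside as a sensitivity analysis, with the number verified and unverified by arm and route.

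I would not add a mailed breathalyzer for remote participants. One reading covers only hours, which is why the plan prompts often and unpredictably during monitoring, and it would not replace PEth.

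**Cost.** Text only, with no new procedure. The stated sensitivity becomes less favourable, and verified-abstinence rates fall in proportion to the abstainers who give no sample. For illustration, a true rate of 30% would be reported as 0.9 × 30% = 27% if 90% of abstainers supply the sample, and as 0.7 × 30% = 21% if 70% do. Showing the self-report result beside it makes that loss visible.

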The first cohort of five participants will complete the tele-health mCM intervention and provide evaluative feedback during an in-depth interview administered at the end of the study, and described in the Measures section below. A coding scheme will be developed for categorizing comments made during the interview based on the study components (e.g., mCM procedures, CBT, interface with smart phone app), subcomponents (e.g., mCM feasibility, CBT burden), and the evaluations drawn (e.g., CBT session too long, video upload still unclear after mCM training).

Successive Cohort Design Stage 2: Treatment Refinement

After the intervention and study have been modified based on information learned from the first cohort, we will treat a second cohort ($n = 5$). Though qualitative data will be evaluated and utilized using methods similar to those of the first cohort, the second cohort will more closely evaluate quantitative data. We will explore relationships of sociodemographic, baseline substance use, and psychiatric comorbidity variables with treatment retention and outcomes. This will identify treatment components to modify or enhance to maximize treatment effectiveness.

Successive Cohort Design Stage 3: Pilot Trial

After treatment modifications from cohort 2, we will conduct a pilot randomized controlled clinical trial. The primary goal of the trial is to evaluate the efficacy of a combined tele-health mCM intervention. The pilot trial will use a two-group design in which 45 participants with an AUD who smoke regularly will be randomized to either:

TELE-HEALTH MOBILE CONTINGENCY MANAGEMENT (mCM) INTERVENTION, a proactive tele-health intervention that combines evidence-based telephone CBT for alcohol and smoking cessation, a tele-medicine clinic for access to nicotine replacement therapy (NRT), and intensive CM therapy administered *via* a smart-phone based application (CM).

OR

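### The 2:1 allocation is justified as maximising power, but this is unsupported in general and incorrect for the common-SD effect measure the plan uses

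*Combined protocol and SAP*

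**What the plan says.** The pilot trial is the third stage of the successive cohort design: "45 participants with an AUD who smoke regularly will be randomized to either" of two arms. The combined protocol and SAP gives two separate reasons for splitting them 30:15.

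- Section C.9.2 (Participant Recruitment, Eligibility, and Screening) gives a reason unrelated to power. "To allow more detailed analysis of the tele-health mCM intervention that is the focus of this study", the third cohort "will randomize 30 participants to the tele-health mCM intervention, and 15 to the tele-health smoking cessation comparison condition".
- Data Analyses, Specific Aim 2, gives a power reason. Because "the tele-health only intervention is expected to have a uniformly small impact on alcohol and smoking outcomes" relative to mCM, a design "with twice as many participants randomized to the tele-health mCM treatment as to the tele-health only treatment" "should maximize power for identifying treatment effects".

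The next sentence puts power at 80% for Cohen's d = 0.76. No alpha, sidedness, SD or abstinence rate accompanies either statement. The planned method is generalized linear modelling, with no link or test statistic named. Outcome Measurement and Biochemical Verification adds a set of binary outcomes: "Self-reported and bioverified prolonged abstinence from alcohol, smoking, and dual abstinence at the 6-month follow-up will be the primary end-point".

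**The concern.** A small mean effect in one arm does not bear on the best allocation ratio. What matters is the relative variance of the outcome in the two arms: with equal variances the even split is optimal, and unequal numbers help only when the larger arm is also the more variable one. The plan states no variance assumption and summarises the effect by one standardised difference.

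At stake is a power property, stated without qualification, that the design is not shown to have. The document describes the pilot as preparation for a grant application, so readers of the plan may take 2:1 as a statistical advantage when, on the plan's own measure, it has a modest cost.

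**Working it through.** **Inputs from the document.** N = 45; arms 30 and 15; d = 0.76; stated power 80%. **Assumed, because not stated:** two-sided 5%, with one-sided variants; abstinence rates; count distribution. The comparator is 23:22, the nearest even split of the same 45.

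**1. The plan's own figure.** For a two-sample t-test, SE = sqrt(1/n1 + 1/n2) in SD units, noncentrality = d/SE, df = 43. At 30:15, SE = sqrt(1/30 + 1/15) = 0.316 and noncentrality = 0.76/0.316 = 2.40. Power is 65.2% two-sided 5%, 76.4% one-sided 5% and 86.4% one-sided 10%. None reproduces 80%. That is a separate matter; nothing below depends on it.

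**2. Allocation with a common SD.** At an exact even split the variance is 4/45 = 0.0889; at 30:15 it is 0.1000. The ratio is 0.1000/0.0889 = 1.125. Equivalently, 4/0.1000 = 40, so 45 participants at 2:1 carry the information of 40 at 1:1.

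| | 30:15 | 23:22 |
|---|---|---|
| SE of difference (SD units) | 0.316 | 0.298 |
| Power at d = 0.76, two-sided 5% | 65.2% | 70.2% |
| Power at d = 0.76, one-sided 5% | 76.4% | 80.6% |
| d detectable with 80% power, two-sided 5% | 0.906 | 0.855 |

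Adjusting for a baseline covariate (correlation 0.3 to 0.6) leaves the even split ahead by 4 to 5 points.

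**3. When 2:1 gains.** Let r be the mCM SD divided by the comparison SD. The two designs tie when r²/30 + 1/15 = r²/22.5 + 1/22.5. Then r² × (1/22.5 − 1/30) = 1/15 − 1/22.5, so r² = 0.0222/0.0111 = 2 and r = 1.41. The optimal allocation ratio equals the SD ratio, so 2:1 is optimal only at r = 2. Welch power at d = 0.76, with the average of the two variances held at 1:

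| r | 30:15 | 23:22 |
|---|---|---|
| 1.00 | 64.1% | 70.2% |
| 1.25 | 67.9% | 70.4% |
| 1.41 | 69.9% | 70.4% |
| 1.50 | 70.9% | 70.4% |
| 2.00 | 74.7% | 70.2% |

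**4. Binary abstinence.** Exact power at assumed comparison v mCM rates, shown as 30:15 v 23:22, two-sided 5%:

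| Test | 5% v 30% | 10% v 40% | 20% v 50% |
|---|---|---|---|
| Fisher | 43.7 v 54.6% | 52.3 v 59.4% | 41.8 v 49.1% |
| Logit Wald | 6.4 v 26.7% | 28.5 v 51.4% | 42.9 v 54.8% |

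At 5% v 30% the score test gives 55.1 v 66.9% and the likelihood-ratio test 61.2 v 68.9%. Over a wider grid (comparison 1–30%, mCM 20–70%), 2:1 never beat the even split on the score, likelihood-ratio or Fisher test; ties occurred only near 100% power. The logit Wald test, run at ten rate pairs, always favoured the even split.

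**5. Counts.** In a simulation with assumed means 14 v 7, gamma-Poisson with shape 1 to 2 and a quasi-Poisson test, power was 59 v 57% and 81 v 81% (30:15 v even), so about equal.

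**The case against.** The strongest defence rests on the word uniformly in "the tele-health only intervention is expected to have a uniformly small impact on alcohol and smoking outcomes". It can be read as saying that outcomes in the comparison arm will vary little, which is the situation in which putting more patients in the other arm helps. A reader might therefore be tempted to go too far in the opposite direction and conclude that 2:1 always costs power. The documents do not support that: they give no SDs, and step 3 shows a real gain once the SD ratio passes about 1.4.

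The abstinence case is also less one-sided than the tests suggest. With binomial SDs sqrt(p(1−p)), the SD ratio is 2.10 at 5% v 30% and 1.63 at 10% v 40%, both above break-even. The SE of the risk difference is then smaller at 30:15: sqrt(0.21/30 + 0.0475/15) = 0.101 v 0.106 at 23:22, and sqrt(0.24/30 + 0.09/15) = 0.118 v 0.121. Only at 20% v 50% (ratio 1.25) is it larger, 0.138 v 0.135. It would thus be wrong to say that every arm contrast has a wider interval. The unpooled normal formula likewise favours 2:1 at 5% v 30% (69.8 v 64.7%). The exact gain for that Wald test is small, however (68.9 v 67.7%), and at a common rate of 10% its type I error is 8.7% at 30:15 against 4.5% at the even split.

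Finally, the stakes are limited. Aim 2 treats the abstinence comparisons as exploratory (although the design section calls efficacy the trial's main goal), and section C.9.2 gives a sound reason for 2:1 that needs no power argument.

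What stands is that the claim cannot be called false under every variance pattern, and that the cost depends on the outcome and test. What does not stand is the unqualified maximisation claim, since no variance condition is stated and the effect is summarised by a common-SD measure.

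**Conclusion.** The claim that 2:1 maximises power is unsupported as written and incorrect for the effect measure the plan uses. With a common SD, 30:15 has 12.5% more variance than an even split and about 5 points less power at d = 0.76 (65% v 70%) if the test is two-sided at 5%, or about 4 points less (76% v 81%) if one-sided at 5%. The usual binary tests agree in direction at the assumed abstinence rates, counts are about neutral, and a gain requires an mCM SD at least about 1.4 times the comparison SD. The binary and count results rest on assumed rates and distributions because the plan gives none.

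A reader might also infer that 2:1 will be carried into the full trial as a supposed efficiency. The document says only that the pilot informs that trial's planning and names no ratio for it, so this is not a finding. Nor does the result show that 30:15 is a poor choice for the pilot: wanting more data on mCM is a legitimate reason to accept a modest loss of power.

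**What to change.** In Data Analyses, Specific Aim 2, delete the rationale that the imbalanced design should maximise power and replace it with:

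> 2:1 allocation is used to give more information on the mCM intervention (n = 30; see Participant Recruitment). Assuming equal variances and a two-sided 5% test, it costs about 5 points of power at d = 0.76 compared with an even split of the same 45 participants; it would gain power only if outcomes are substantially more variable in the mCM arm.

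If the investigators did mean that comparison-arm outcomes will be less variable, they should state the SD ratio they expect and its source. The cost is a couple of sentences and a slightly less favourable account of the design. The ratio, enrolment, procedures and analysis are unchanged.
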